## 6. STUDY SETTING

After participant recruitment, the study assessments will take place at University College London Hospitals (NHS Foundation Trust) (participants from all groups) or UCL Ear Institute (participants from ARHL and control groups only). The participants for this study will be recruited from:

- University College London Hospitals (NHS Foundation Trust) (siderosis group)
- Adult Audiology Centre, University College London Hospitals (NHS Foundation Trust) (ARHL group)
- The general public (ARHL and control groups): will be recruited from University College London Hospitals (NHS Foundation Trust) waiting areas, canteens, cafeterias, BRC BioResource group, AgeUK group, the University of Third Age and dedicated Facebook/social network and online groups

The clinical equipment available at the Adult Audiology Services at University College London Hospitals (NHS Foundation Trust) or provided by the UCL Ear Institute, will be used to conduct this study. No additional equipment will be provided to sites for the purposes of the study since all the tests in this protocol are already available to the NHS users with hearing impairment, poor coordination or cognitive impairment. The facilities at the Ear Institute permit hearing tests to take place. These can be conducted by the research student and be undertaken by the participants with minimal risk of balance problems and minimal risks of falls such as the ARHL group and control group participants.

## 7. SAMPLE AND RECRUITMENT

### 7.1 Eligibility Criteria

Potential participants will be identified by a member of the relevant clinical team or recruited from the general public, and according to the inclusion/exclusion criteria as outlined below. The recruitment will take place simultaneously for all three groups of participants.

#### 7.1.1 Siderosis group

Inclusion criteria:

- Adults (male and female) of 18+ years old with a known diagnosis of iSS confirmed by a consultant neurologist with expertise in this condition at University College London Hospitals (NHS Foundation Trust)

Exclusion criteria:

- Individuals with a physical or mental impairment that prevents the potential participant from giving informed consent or undergoing the audiological and/or vestibular assessment
- Individuals younger than 18 years old
- Individuals with no prior diagnosis of iSS

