## 4.2 Outcome questions

Primary outcome question: What are the salient and disease-specific features of auditory and vestibular dysfunction and what is the impact of iSS on olfactory and cognitive functions and on the quality of life?

Secondary outcome question: How do the imaging findings correlate with the results of audiological, cognitive and vestibular assessments and severity of symptoms?

Tertiary outcome question: Which audiological tests are able to better predict auditory impairment in iSS group compared to the ARHL and the control groups?

Quaternary outcome question: Can a combination of auditory testing approaches be used as a valid functional tool for hearing assessment and site of lesion testing in patients with auditory dysfunction based on the findings of the cohorts included in this study?

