**Comparison:**

The findings obtained following the audiological and the quality-of-life questionnaires will be compared between the siderosis group, the ARHL group, and the control group. The results of vestibular assessments will be compared to the age-matched normative data.

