#### 7.1.2 Age-related hearing loss (ARHL) group

Inclusion criteria:

- Adults (male and female) of 18+ years old with a known diagnosis of ARHL

Exclusion criteria:

- Individuals with a physical or mental impairment that prevents the potential participant from giving informed consent or undergoing the audiological assessment
- Individuals younger than 18 years old
- Individuals with diagnosis of hearing loss of aetiology other than age-related

- Individuals with history of exposure to high-intensity noise or ototoxic drugs or evidence of middle ear disease/dysfunction or family history of non age-related hearing loss
- Individuals with no previous diagnosis of age-related hearing loss

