## 7.2 Sampling

### 7.2.1 Size of sample

Power and sample size calculations cannot be reliably carried out prior to commencing the study as we are restricted by how rare the disease is. Furthermore, there are currently few reports on audiological and vestibular function in iSS in the literature, and where available, these are highly heterogeneous in the testing regimens used. There appears no primary test or indicator that is considered the 'gold standard' test. This heterogeneity means that it is challenging to effectively perform necessary power/sample size calculations. In addition to this, a comprehensive battery of tests will be included in this study, each of which will influence the required sample sizes. Due to its rarity we would like to recruit as many participants with iSS as possible. Reviewing the study for feasibility, however, after 10-15 participants in each arm have been assessed in the study, will allow to establish the variability between the groups and will be used to inform the adjustment to sample size. Furthermore, it will be likely to reflect on the difficulty (or ease) as well as the pace of recruitment of participants into the study.

These preliminary results will be collected and analysed by the research student in collaboration with a designated biostatistician from the UCL and the Biostatistics Office at UCL(H) JRO. A validated statistical software programme will be used to conduct the analysis, which will include all the parameters and assumptions used in the pilot study. Inflation factors and attrition rate will also be accounted for and will be included into sample size calculations.

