## 8.1 Assessment and management of risk

### Risks and burdens of participation in the study:

Participants in this research study will have minimal risk of harm or burden, as the assessments that the participants will undergo in the course of this study are already in the current clinical practice in the NHS and these are associated with minimal risk of adverse events.

The minimal risks that may arise from participating in this study include: (a) risk of minimal discomfort from undergoing the battery of tests and assessments as part of this study (b) risk of possible misunderstanding between the participant and the student researcher, (c) risk of breach of confidentiality, (d) risk of possible mishandling of participants' personal data.

- (a) The clinical, audiological, vestibular assessments may be perceived as uncomfortable by the participants, yet these assessments constitute the standard current clinical practice within the NHS. Should the participant express their wish not to continue with any of the assessments or with further participation in the study, the assessment or the participant's involvement in the study will be terminated with no further repercussions to the participant's provision of clinical care or clinical follow-up, and data not obtained as a result of this will be recorded as missing.
- (b) To minimise the possibility of a misunderstanding between the participants and the research student, the participants and their next-of-kin will be encouraged to ask questions and seek clarification at any point in the course of their participation in the study.

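### Inability to do vestibular tests alone bars a siderosis patient from the whole study, which may select milder iSS into hearing, quality-of-life and imaging analyses that do not depend on those tests

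*Combined protocol and SAP*

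**What the plan says.** Section 7.1.1 (siderosis group) excludes people whose physical or mental impairment stops them giving consent or "undergoing the audiological and/or vestibular assessment". The matching criterion in section 7.1.2 (ARHL) covers an impairment that "prevents the potential participant from giving informed consent or undergoing the audiological assessment". Section 7.1.3 (controls) likewise names only the audiological assessment.

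Section 5.2, under Comparison, says that the audiological findings and "quality-of-life questionnaires will be compared between the siderosis group, the ARHL group, and the control group". Vestibular findings take a separate route: "The results of vestibular assessments will be compared to the age-matched normative data".

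The primary outcome question in section 4.2 covers auditory and vestibular features and also asks "what is the impact of iSS on olfactory and cognitive functions and on the quality of life". On recruitment, section 7.2.1 says "Due to its rarity we would like to recruit as many participants with iSS as possible", and section 7.2.2 caps the group at 30.

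The plan accepts incomplete batteries in two other settings. Section 7.3.1 drops language-dependent tests for participants with poor English. Section 8.1 says that if a participant asks to stop an assessment, "data not obtained as a result of this will be recorded as missing".

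**The concern.** The condition applies to one group only, and along a dimension of the disease itself. Section 2 lists imbalance and ataxia, with hearing loss, as the commonest clinical features of iSS. The siderosis battery in section 5.2 includes a gait test with turns, stairs and obstacles, fast head rotations, and nystagmography or rotational-chair testing. An impairment that prevents these is plausibly related to severity. If so, three things follow:

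- The siderosis group looks milder than it should against ARHL and controls on hearing and quality of life.
- The correlations of function with imaging (objective 2) are estimated over a narrower range of severity.
- The vestibular results leave out, without a count, the patients who could not be tested.

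The wording is also loose. It does not say whether one undoable test or an undoable battery triggers the exclusion, so two assessors could apply it differently.

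**Working it through.** **1. What the rule does.** Under 'and/or', either inability is sufficient. No section allows entry for the hearing, questionnaire, smell or imaging parts alone.

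**2. Which analyses need vestibular testability.**

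| Analysis | Needs vestibular tests? |
|---|---|
| Three-group hearing comparison (5.2, Comparison) | No |
| Three-group quality-of-life comparison (5.2, Comparison) | No |
| Olfactory and cognitive parts of the primary question (4.2) | No |
| Imaging against auditory function (4.1, objective 2) | No |
| Imaging against vestibular function (4.1, objective 2) | Yes, but could use the tests that were done |
| Vestibular results against normative data | Yes |

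**3. Whether another provision lets such patients in.** The missing-data rule in section 8.1 applies to people already taking part. Section 8 (reimbursements) has the research student check suitability and take consent straight after the clinic appointment, which is the visit at which section 5.2 places nystagmography/rotational chair and head-impulse testing. Section 5.2 also lists consent first at that visit, so the order is not settled. On the section 8 order, inability would be known before the missing-data rule could apply.

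**4. Whether the selection could be counted.** Section 7.3 sends siderosis ineligibility reasons to the medical notes, whereas control-group reasons go to the study file. No study-level log is stated for siderosis patients.

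**5. Size.** The plan gives no power, alpha, effect size or share excluded, so there is no figure of its own to reproduce. What follows is illustrative. Let f be the share of otherwise eligible iSS patients excluded for vestibular inability alone, and d their mean deficit in SD units relative to those included. The mean over all eligible patients is (1 − f) × included + f × excluded, so the included group looks milder by

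shift = f × d.

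| f (assumed) | d = 0.5 | d = 1.0 | d = 1.5 |
|---|---|---|---|
| 5% | 0.025 | 0.05 | 0.075 |
| 10% | 0.05 | 0.10 | 0.15 |
| 20% | 0.10 | 0.20 | 0.30 |
| 30% | 0.15 | 0.30 | 0.45 |

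The standard error of the siderosis mean in SD units is 1/√n: 1/√20 = 0.22 and 1/√30 = 0.18. At d = 1.5 the shift passes the standard error once f exceeds 0.183/1.5 = 12% (n = 30) or 0.224/1.5 = 15% (n = 20). At d = 0.5 it does not do so anywhere in the table. For a contrast of two equal groups the standard error is √(2/n), or 0.26 to 0.32, so the shift weighs less there.

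**6. Upper bound.** Suppose the rule removed exactly the most severe 10, 20 or 30% on the outcome itself (normal distribution). The mean shift is φ(z)/(1 − f), where z is the cut-off: 0.1755/0.9 = 0.20, 0.2800/0.8 = 0.35 and 0.3477/0.7 = 0.50 SD. A true imaging-function correlation of 0.50 would fall to 0.44, 0.40 or 0.38. These are ceilings, because they treat vestibular inability as identical to severity on the outcome. If the two correlate at an assumed 0.3 to 0.5, the shifts shrink in proportion, to 0.06-0.10, 0.11-0.18 and 0.15-0.25 SD.

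**7. Precision.** If exclusions cut 30 per group to 24 (a 20% loss, groups kept equal), the difference detectable with 80% power at two-sided 5% rises from (1.960 + 0.842) × √(2/30) = 0.72 SD to 2.802 × √(2/24) = 0.81 SD by the normal approximation. If 30 eligible patients are still found, it does not change.

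**The case against.** Several points on the other side carry weight.

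- **Vestibular function is central.** It is in the study title, aim 2 and the primary outcome question, so requiring that it can be assessed is coherent, and the comparators lack the condition because they have no vestibular tests. This explains why the tests are given. It does not explain why a patient who cannot do them should leave every other analysis.
- **The rule concerns prevention, not poor performance.** Most of the battery records eye movements or muscle responses, and the ataxia scale is designed for ataxic patients. Section 6 notes that the tests are already offered to people with poor coordination. A reader might infer that the most disabled patients are lost. The documents do not show this: the share is unstated and could be near zero.
- **Recruitment is capped.** A reader might set the rule directly against the wish to recruit as many as possible, or conclude that power falls. Section 7.2.2 stops at 30, the exclusion acts before enrolment, and section 1 reports a 65-patient iSS cohort from the neurology hospital. Nothing shows that the eligible pool is the limiting factor. The selection would remain even at 30.
- **The allowances for incomplete testing are analogies.** One concerns English and the other an enrolled participant's wish to stop. They show that the analysis can tolerate gaps, but they do not contradict the entry rule.
- **Direction.** For the hypothesis of a greater speech-in-noise deficit in iSS (section 2), milder selection makes a positive contrast conservative. That does not help where the aim is to describe the disease profile or its effect on quality of life.

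**Conclusion.** The point holds as a design weakness that should be corrected. The text makes vestibular inability alone a study-level exclusion for the siderosis group only, leaves its trigger undefined, and offers no partial entry. The three-group hearing and quality-of-life contrasts make no use of vestibular data, so the restriction buys them nothing and may tilt them towards milder iSS.

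The size is unknown. Under the assumed shares and deficits it runs from negligible (0.03 SD) to about twice the standard error of the siderosis mean (0.45 against 0.18-0.22 SD). That severity drives the exclusion is a reasonable inference from section 2, not a documented fact. Neither a certain loss of the most severe patients nor a certain loss of power is supported. The case rests on the wording and scope of the rule rather than on the illustrative figures.

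**What to change.** - In section 7.1.1, limit the exclusion to inability to consent or to undergo the audiological assessment, matching section 7.1.2.
- State that patients who cannot do some or all vestibular tests may join for the hearing, questionnaire, smell and imaging parts.
- Record each vestibular test not done as 'not testable' with its reason. Analyse vestibular outcomes in those tested, and report the not-testable counts beside them.
- In section 7.3, log siderosis ineligibility reasons in the study file as well as the medical notes, so that numbers screened and excluded can be reported.

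The cost is a protocol amendment and more missing vestibular data, which must be reported openly. If the cap of 30 binds, slightly fewer participants will have complete vestibular results.

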#### 7.1.2 Age-related hearing loss (ARHL) group

Inclusion criteria:

- Adults (male and female) of 18+ years old with a known diagnosis of ARHL

Exclusion criteria:

- Individuals with a physical or mental impairment that prevents the potential participant from giving informed consent or undergoing the audiological assessment
- Individuals younger than 18 years old
- Individuals with diagnosis of hearing loss of aetiology other than age-related

- Individuals with history of exposure to high-intensity noise or ototoxic drugs or evidence of middle ear disease/dysfunction or family history of non age-related hearing loss
- Individuals with no previous diagnosis of age-related hearing loss

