## 2. RATIONALE

Presence of progressive and disabling sensorineural hearing loss (SNHL), imbalance and ataxia are the most common clinical features associated with iSS (8). Yet few reports in the literature provide a detailed description of these characteristics. We hypothesise that due to limited knowledge, iSS is likely to be under-recognised in the clinical setting, and thus under-diagnosed and under-reported. Further studies with larger patient cohorts and comprehensive battery of audiological and vestibular tests are required to gain greater understanding and knowledge regarding functional deficits in iSS.

Literature reports describe the pattern of hearing loss in iSS on pure-tone audiometry (PTA), to be similar to age-related hearing loss (ARHL) – down-sloping pattern with the initial loss at higher frequencies. What differentiates the auditory impairment in iSS, is the asymmetrical pattern and earlier onset of hearing loss than expected for ARHL(10). Similarities of pattern of hearing impairment between iSS and ARHL are likely to lead to iSS being misdiagnosed, and may result in disease progression and delayed diagnosis. When assessing the auditory function in iSS with ABR, speech audiometry and stapedial reflex testing, the literature suggests that hearing loss is of retro-cochlear origin.

Due to the lack of reports of comprehensive audiological assessment, the distinct pattern of hearing impairment in iSS patients remains to be elucidated. We hypothesise that the audiological profile of patients with iSS differs from that of individuals with ARHL and that a specific and pathognomonic audiological pattern attributable to iSS may exist. We further hypothesise that pure tone audiometry alone cannot reliably characterise the hearing dysfunction in iSS and that the use of extended audiometric battery of tests is needed to identify the precise audiological deficits in iSS.

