### 3. THEORETICAL FRAMEWORK

Because our knowledge of the impact of iSS on hearing and balance is limited and due to progressive and significant morbidity associated with this condition, there is a clear need to improve our understanding of audiovestibular dysfunction and determine its disease-specific pattern. Early recognition of iSS in the clinical setting will enable prompt efforts to halt disease progression by means of initiation of treatment and rehabilitative measures and as a consequence, likely reduction in the associated morbidity.

Extensive battery of hearing tests, including self-report questionnaires, undertaken by the participants will identify test-specific deficits and will reflect which of the tests or their combination best characterise auditory dysfunction in iSS, how these deficits compare to the auditory characteristics in the ARHL group, and which tests most accurately identify hearing dysfunction in both groups. The use of self-report questionnaires in combination with the psychophysical tests will further characterise the auditory and vestibular dysfunction and are thus likely to better reflect functional deficits specific to iSS and ARHL than by means of objective tests alone.

This analysis will achieve a dual goal: firstly, we will be able to determine the disease-specific pattern of hearing loss in iSS and how it compares to age-related hearing loss; and secondly, we will be able to determine which tests or their combination best reflect auditory dysfunction in patients with hearing impairment and are thus likely to be used as markers of function and outcome measures in assessment of sensorineural hearing loss. By employing an extended battery of audiological tests and their combination, we will also attempt to stratify patients with hearing problems based on the likely site of pathology of the auditory pathway and identify those with peripheral deficits from patients with central deficits.

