### 7.1.3 Control group

Inclusion criteria:

- Adults (male and female) of 18+ years old with no previous diagnosis of hearing loss or no known neurological disorder (including iSS) that affects hearing (control group); we will aim to recruit such participants of 50 years of age and above, however if difficulty with recruitment of such participants arises, we will recruit participants of 18 years of age and above.

Exclusion criteria:

- Individuals with a physical or mental impairment that prevents the potential participant from giving informed consent or undergoing the audiological and assessment
- Individuals younger than 18 years old
- Individuals with a known history of hearing loss (of any cause) or with a known neurological disorder that affects their hearing
- Individuals with history of exposure to high-intensity noise or ototoxic drugs or evidence of middle ear disease or family history of non age-related hearing loss

Participants in the siderosis group will be users of the National Health Service (NHS) and will be recruited from University College London Hospitals (NHS Foundation Trust) London. The ARHL group participants will be recruited from the Adult Audiology Services at University College London Hospitals (NHS Foundation Trust), and will have used the NHS services in the past or will be recruited from the general public. The control group participants will be recruited from the general population. There will be no upper limit to the participants' age.

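### The ARHL exclusions do not cover a co-existing known neurological disorder in someone whose hearing loss is labelled age-related, although this group is the main comparator for the retro-cochlear question

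*Combined protocol and SAP*

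**What the plan says.** Section 7.1.2 admits "Adults (male and female) of 18+ years old with a known diagnosis of ARHL". Two of its exclusions concern the cause of the loss. One removes "Individuals with diagnosis of hearing loss of aetiology other than age-related". The other removes "Individuals with history of exposure to high-intensity noise or ototoxic drugs or evidence of middle ear disease/dysfunction or family history of non age-related hearing loss". No item in the section mentions neurological disease.

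Section 7.1.3, for controls, excludes "Individuals with a known history of hearing loss (of any cause) or with a known neurological disorder that affects their hearing". The control inclusion criterion also refers to neurological disorders and names iSS as an example. The noise, ototoxic-drug, middle-ear and family-history item appears in almost the same form in both sections. The neurological item appears only for controls, and no reason is given.

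The ARHL group carries the main auditory comparison. Section 2 states: "We hypothesise that the audiological profile of patients with iSS differs from that of individuals with ARHL". Section 3 sets out to "identify those with peripheral deficits from patients with central deficits". Section 4.2 asks whether a combination of auditory tests can serve for site-of-lesion testing.

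**The concern.** The scientific claim at stake is that iSS has a distinct, probably retro-cochlear, auditory pattern that ordinary age-related loss does not share. The evidence would come from ABR, acoustic reflexes and speech-in-noise. A neurological disorder of the auditory pathway can disturb these tests while the audiogram still looks age-related and the ARHL label stays in place.

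An ARHL participant of that kind would make the comparator look more like iSS. The hypothesis in section 2 of a larger speech-in-noise deficit in iSS after controlling for hearing deficits does not escape this, because adjusting for the audiogram cannot remove a central deficit that the audiogram does not show. With 20 to 30 people per group (section 7.3), one or two participants can visibly move an observed specificity.

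**Working it through.** The protocol gives no figure on this point and section 7.2.1 declines a power calculation, so there is no stated number to reproduce. The check is mainly a comparison of texts.

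**Who is eligible for the ARHL group?**

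| Candidate with an ARHL label | Under 7.1.2 as written |
|---|---|
| Hearing loss also diagnosed as neurological in origin | Excluded by the aetiology item |
| Known neurological disorder of the auditory pathway, loss attributed to age only | Eligible |
| Undiagnosed central disease, including unrecognised iSS | Eligible |

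The second row is the gap addressed here. The protocol's own drafting shows that a rule about the cause of hearing loss is not treated as a substitute for a rule about co-existing exposure or disease. Section 7.1.3 excludes hearing loss of any cause and still lists neurological disorder. Section 7.1.2 has the aetiology item and still lists noise, ototoxic drugs and middle-ear disease.

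**Does a later step catch it?**
- Section 5.2 includes a full medical history and neuro-otological examination at the ARHL visit, and section 7.3 settles eligibility there. No criterion tells the researcher to act on neurological history.
- ABR and reflexes are measured in ARHL participants, but no eligibility or analysis rule uses the results.
- Imaging is described for siderosis patients only (5.2).
- Section 5.5 specifies regression models and chi-square tests, with no sensitivity analysis for this group.

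**Scale (illustration only).**

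Specificity in the ARHL group = participants without the sign ÷ n. Each participant who has the sign because of a co-existing disorder lowers it by 1/n:
- n = 20: 1/20 = 5 points; two such participants, 2/20 = 10 points.
- n = 30: 1/30 = 3.3 points.

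For a continuous test, let d be the true standardised iSS–ARHL difference and c the share of ARHL participants whose results are, on average, like those in iSS. The expected difference becomes d × (1 − c). With SD 1, n per group and two-sided alpha 0.05, approximate power is Φ(d(1 − c)√(n/2) − 1.96). For an assumed d = 0.8 and n = 20, √(20/2) = 3.162:
- c = 0: Φ(2.530 − 1.96) = 71.6%
- c = 1/20 = 5%: Φ(2.403 − 1.96) = 67.1%
- c = 2/20 = 10%: Φ(2.277 − 1.96) = 62.4%

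With n = 30 the same values of c give 87.3%, 83.7% and 79.6%. Neither d nor c comes from the documents. These lines show what one or two people in 20 would do, not how many there are.

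**The case against.** The strongest reply is that 7.1.2 already does most of the work. A neurological disorder diagnosed as the cause of the hearing loss is a cause other than age, so that person is out. This stands. A reader who sees neurological disease named for controls only might infer that the ARHL group has no protection against it; the aetiology item rules that reading out.

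A second reply is that controls are not fully protected either, since their rule is limited to a known disorder that affects hearing. This also stands. It means that copying the control wording unchanged would not be enough: where the loss has been put down to age, nobody may have recorded that the disorder affects hearing, and the person could still enter.

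A third reply is that ARHL patients with comorbidity belong to the population from which iSS must be told apart in practice, so removing them could flatter specificity. This is a fair point about generalisability. However, the protocol has already chosen a clean ARHL group by excluding noise, ototoxic drugs and middle-ear disease, and a neurological item is consistent with that choice.

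A fourth reply is that the history and examination at the visit let a clinically trained researcher notice such cases. They do, but without a criterion the handling is left to discretion.

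**Conclusion.** The gap is real and narrow: section 7.1.2 does not address a known neurological disorder that co-exists with hearing loss labelled age-related, and nothing later in the plan does so. If such participants enter and their results resemble those in iSS, the bias is towards no iSS–ARHL difference and towards lower apparent specificity. It would not manufacture an iSS signature.

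The size is unknown. A reader might infer that a material share of the ARHL group is affected; the documents give no prevalence, no abnormality rates and no effect size, so no percentage can be defended. The 5 points per participant in a group of 20 assumes that the participant has the sign and would not have had it without the disorder.

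This is a modest weakness in the definition of the comparator. It is worth correcting because the remedy is cheap.

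**What to change.** Add one exclusion to 7.1.2, adapted from the inclusion criterion of 7.1.3 (which names iSS) and its exclusion criterion (which does not):

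*Individuals with a known neurological disorder (including iSS) that affects or could affect the central auditory pathway, whether or not their hearing loss has been attributed to it.*

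Check it from the medical history already taken at the ARHL visit, before the hearing tests. For any ARHL participant already enrolled who meets it, report the iSS-versus-ARHL comparison with and without that person. The trigger must be the history, not the ABR or reflex results: removing people because of the outcome tests would bias the comparison towards a difference.

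The cost is a protocol amendment of one line and no new test. A few volunteers become ineligible, which recruitment from both the clinic and the general public should absorb. Two limits should be stated in the report. Undiagnosed central disease, including iSS mislabelled as ARHL (which section 2 itself expects to happen), is not caught. Any specificity then applies to ARHL without known neurological disease of this kind.
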